#### INTENSITY OF AES

The intensity of the AE will be characterized as Grade 1 -5 according to the NCI CTCAE 4.03:

Grade 1: Mild; asymptomatic or mild symptoms; clinical or diagnostic observations only; intervention not indicated.

Grade 2: Moderate; minimal, local or noninvasive intervention indicated; limiting age-appropriate instrumental activities of daily living (ADL).

Grade 3: Severe or medically significant but not immediately life-threatening; hospitalization or prolongation of hospitalization indicated; disabling; limiting self care ADL.

Grade 4: Life-threatening consequences; urgent intervention indicated.

Grade 5: Death related to AE.

When the intensity of the AE changes over time, the maximum intensity will be recorded.

#### RELATIONSHIP TO DEFINITY ADMINISTRATION

The relationship or association of the AE to the Definity administration will be characterized as "unlikely," "possible," or "probable." A relationship assessment will be performed by the investigator to determine if an AE is attributable to Definity and will be recorded on a data form. The investigator will refer to the Definity Package Insert for assistance in determining AE relationship.

An "unlikely" relationship indicates that there is little or no chance that Definity caused the reported AE; other conditions, including concurrent illnesses, progression or expression of the disease state, or a reaction to a concurrent medication, appear to explain the reported AE.

A "possible" relationship indicates that the association of the AE with Definity is unknown. However, the AE is not reasonably attributed to any other condition.

A "probable" relationship indicates that a reasonable temporal association exists between the AE and Definity administration and, based upon the investigator's clinical experience, the association of the event with the trial medication seems likely.

#### SERIOUS ADVERSE EVENTS

A "serious" AE (SAE; Grades 3-5) is defined as a significant clinical hazard, contraindication, or precaution that:

- Results in death
- Is life-threatening (In the opinion of the investigator, there is an immediate risk of death from the AE as it occurred. This does not include an AE that had it occurred in a more serious form may have caused death.)
- Results in a persistent or significant temporary disability/incapacity defined as a substantial disruption of a person's ability to conduct normal life functions
- Results in or prolongs an existing in-patient hospitalization (an overnight stay in the hospital, regardless of length) [Note: A hospitalization for an elective procedure or treatment which is not associated with an AE, hospitalization for a pre-existing condition which did not worsen, and hospitalization for reasons of convenience or observation, do not constitute an SAE.]
- Is a congenital anomaly/birth defect (in offspring of a subject taking the trial medication, regardless of time to diagnosis)
- Is an important medical event that may not result in death, be life-threatening, or require hospitalization but based upon the appropriate medical judgment, the event may jeopardize the subject and may require medical or surgical intervention to prevent one of the outcomes listed for the definition of a serious adverse experience.

All unexpected and serious adverse events are reported to the TJU/UCSD IRB and to FDA if applicable. The investigator is required to submit all unexpected and serious adverse events to the TJU/UCSD IRB

and the data safety monitoring board within 48 hours. Fatal adverse events related to treatment which are unexpected must be reported within 24 hours to the TJU/UCSD IRB and the DSMB through CRMO.

The written report for any SAEs that occur during the study, whether or not related to the Definity administration will be submitted immediately (within 24 hours) to the TJU (or UCSD) Institutional Review Board.

The designated medical monitor will review all serious and unexpected adverse events associated with the protocol and provide an unbiased written report of the event within 10 calendar days of the initial report. At a minimum, the medical monitor will comment on the outcomes of the adverse event and relationship of the event to the Definity administration.

A copy of the SAE will be retained on file with the respective subject's data forms.

## 6.9 End-of-Treatment and End-of-Trial Evaluations

### 6.9.1 Discontinuation of Subjects

Subjects will be free to discontinue trial participation at any time. The investigator will also discontinue any subject from the trial if, in the investigator's opinion, it is not safe for the subject to continue. The date the subject is withdrawn from a treatment and/or from the trial and the reason for discontinuation will be recorded on the CRF.

Trial participation will be considered completed if the subject has met all of the following trial requirements:

- Has received two injections of Definity
- Has undergone the complete US imaging study (baseline and contrast-enhanced) as described in this protocol
- Undergoes a breast biopsy (core / excisional / lumpectomy) or mastectomy within 30 days of the contrast-enhanced US imaging study

If a subject's participation in the trial is interrupted for any reason (e.g., because of an AE or if the subject is lost to follow-up) and the subject has met the criteria described above for completing the trial, the subject's trial participation will be considered completed. If a subject's trial participation is

interrupted for any reason by the subject's or investigator's choice and the subject has not met all of the criteria listed above, then the subject will be considered a discontinued subject.

## 7 DATA MANAGEMENT AND STATISTICAL ANALYSES

### 7.1 Data Management

Data forms will be completed for all subjects enrolled in the trial. The patient study files will be stored in a secure file cabinet and maintained by the research study coordinator. Patient study files will be kept for 7 years after the completion of the study.

The final data will be entered into a database. The investigator will be responsible for management of the database. The database will be maintained within an organized and secure directory system.

### 7.2 Statistical Analyses

#### 7.2.1 Hypotheses:

H1: SHI or pulse inversion HI will improve the diagnostic accuracy of mammography, grayscale US or power Doppler imaging to distinguish benign from malignant breast disease. The fundamental hypothesis is that the area under the ROC curve will improve by 0.10 to 0.15 with SHI compared to the other imaging modalities.

H2: Some findings of SHI (including perfusion estimates and CMI-SHI) or pulse inversion HI correlate with the pathological diagnosis of benign/malignant or with other significant physiological/pathological parameters. The fundamental hypothesis is that higher correlation coefficients can be achieved with SHI than with pulse inversion HI.

H3: 3D SHI estimates of perfusion correlate with absolute perfusion measured in the kidneys of dogs. The fundamental hypothesis is that correlation coefficients above 0.75 can be achieved for *in vivo* SHI perfusion estimates.

H4: *In vivo* fractional tumor vascularity measurements obtained with power Doppler imaging, pulse inversion HI or SHI correlate with iMVD or any other pathological measure of breast tumor vascularity obtained in the surgical biopsy specimens. The fundamental hypothesis is that higher correlation coefficients can be achieved with SHI than with the other two US flow modes.

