Initial results using contrast enhanced SHI have been promising. As part of a federally funded pilot study using both Definity and Optison (GE Healthcare, Princeton NJ), we have demonstrated, in 14 women with 16 lesions (out of which 4 were cancers) that SHI can detect the slow, small volume blood flow associated with breast tumor angiogenesis [Forsberg et al 2005; 2007]. SHI resulted in an almost complete suppression of tissue signals allowing better visualization of the lesion vascularity relative to baseline power and improved display of small intra-tumoral vessels relative to PDI. The internal morphology of the vascularity associated with the breast masses were also visualized better with SHI than with contrast enhanced PDI. Additionally, we found that the area under the ROC curve for the diagnosis of breast cancer was higher for SHI than for any of the other techniques tested (0.78 versus 0.64, 0.67 and 0.76) [Forsberg et al 2007].

For quantitative analyses, SHI time intensity curves were determined within each lesion using ImagePro Plus software (Media Cybernetics, [name]) [Forsberg et al 2006a]. SHI perfusion estimates were determined using the linear relationship previously established in a canine model [Forsberg et al 2006b]. Perfusion estimates were determined within three regions of interest, (ROIs) encompassing the centre, the periphery or the entire breast lesion. SHI perfusion estimates within the entire lesion were significantly different for malignant and benign tumors ( $p = 0.04$ ) but not for central and peripheral ROIs ( $p > 0.32$ ).

Further quantitative information on the vascular morphology can be extracted post-acquisition by the construction of cumulative maximum intensity (CMI) images from SHI clips. In CMI mode a composite image depicting vascular architecture and blood flow is constructed through maximum intensity projection (MIP) of SHI data over consecutive images [Dave & Forsberg 2009]. Using CMI-SHI the area under the ROC curve was found to be significantly higher than mammography ( $p=0.031$ ) and the highest level of all methods discussed above with an  $ROC=0.90$  [Dave et al 2010]. Using this technique we have

created parametric images of US contrast kinetic data acquired over a specific time sequence (from contrast injection to washout) showing localized variations in these parameters within a plane and potentially providing additional post-acquisition data for lesion differentiation [Eisenbrey et al 2010].

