## 6.6 Efficacy Assessments

The primary blinded read will be performed on all 450 human cases by a physician with more than 15 years of expertise in general breast imaging and with specific expertise in breast SHI ([name]). All imaging studies will be rated on a quasi-continuous scale from 0 to 100 ranging from “no lesion seen (no findings)” over “probably benign” and “indeterminate” to “malignant.” Using a quasi-continuous 100-point rating scale has an intuitive probabilistic interpretation and is known to improve the assessment of the characterization capabilities of the imaging modes studied [Wagner et al 2001].

The SHI images will be qualitatively analyzed as described above for the pulse inversion HI injection. The pre- and then post-contrast diagnostic US criteria (as detailed below) will be evaluated for each patient in two readings as follows: grayscale; grayscale and PDI (baseline); grayscale and contrast enhanced pulse inversion HI, and then in the second reading grayscale/baseline and SHI and, finally grayscale and SHI with dynamic CMI-SHI added. While this may introduce some bias from pre- to post-contrast results, we considered this the more realistic approach to how US contrast may be used in clinical practice. Moreover, such a “sequential” reading scheme may well produce the same total reader variance as a more independent reading scheme (where the evaluation of each imaging mode is separated in time by 1 month or more), while having the advantage of being logically much less demanding [Beiden et al 2002]. Each case will also be read by the two on-site investigators, blinded to the mammographic and histopathological diagnosis, to allow repeatability to be assessed for each site. Finally, each mammogram will be read by a radiologist as part of the patient’s standard clinical assessment and assessed using the BIRADS scale [ACR 1998].

Diagnostic US criteria (Evaluated for each imaging mode):

- Diagnosis; size, shape, and orientation of the lesion; echogenicity compared to surrounding tissue.

- Distribution of color signals and the overall color content of the lesion evaluated by comparing the pattern and amount of color to the normal surrounding breast.
  - If uniform, the color will be categorized as less intense, iso-intense or more intense than normal breast.
  - If non-uniform, the color will be described by location, intensity and distribution.

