## 6.7 Pathology

All subjects will be scheduled to undergo a breast biopsy (core / excisional / lumpectomy) of the mass or region of abnormality or mastectomy within 30 days after the US study procedure. The date of the biopsy and the pathology results will be recorded. An experienced pathologist will complete a worksheet for each biopsy specimen. If the patient undergoes a surgical biopsy at TJU, the surgeon will mark the transaxial plane of the lesion by sutures upon excision of the breast mass. At UCSD surgical biopsy specimens will be treated according to clinical standard i.e., the imaging plane and the pathology sections will not be matched. Careful attention will be paid to the labeling of each section to ensure the correct orientation. Whole mount paraffin blocks will be prepared from which central 5 mm sections will be cut and mounted on 2 x 3 inch glass slides and stained with hematoxylin and eosin (H&E) according to standard methods and examined microscopically by the pathologist as part of the patient's clinical care. Apart from diagnosis, the pathologist will provide the following variables: estrogen progesterone and HER2 receptor presence or absences; presence or absence of hemorrhagic, necrotic, or other component of the lesion (and their location if present); histological margins; lesion size; TNM staging; histological lesion type; presence or absence of vascular invasion; histological and cytological grade; presence or absence of metastases; node staging; and percentage of the lesion that was invasive or *in situ*. If the

patient undergoes a core biopsy, it will not be possible to assess lesion size. All other histopathological parameters will be the same as for the excisional biopsy described above and the specimens will be treated identically.

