All histopathological variables will be compared to imaging judgments on diagnoses and characteristics of vascularity for the different modalities. When both sets of variables are nominal, chi-square tests will be conducted. When both types of variables are ordinal or continuous, correlations will be calculated. When one type of variable is nominal and one continuous non-parametric rank order tests such as Mann-Whitney U-tests or Kruskal-Wallis tests will be performed [Rosner 1990]. Inter- and intra-observer variability will also be determined by calculating the intraclass correlation coefficient and the kappa statistic [Shrout 1979; McGraw 1996].

Comparisons of sensitivities, specificities and accuracies for diagnosing cancer with the different imaging modalities will be conducted with McNemar's test for correlated proportions (against the histopathological gold standard). All of the statistical analyses proposed for the human clinical trial will be repeated split by racial and ethnic groups to determine if clinically important race/ethnicity differences exist in the ability of 3D SHI to diagnose breast cancer.

Finally, the vascularity measures obtained from the subgroup of up to 85 CD31 stained breast tumor specimens will be compared to the fractional tumor neovascularity data to determine if any correlation exists (in baseline PDI or one of the two contrast enhanced modes). The existence of a linear relationship between ultrasonic and pathologic data will be assessed using single variable linear regression techniques and reverse stepwise multiple linear regression analysis.

All analyses and computations will be performed using NCSS/PASS 2005 and Stata 9.0 (Stata Corporation, College Station, TX), while the study database will be designed and implemented in Filemaker Pro 10.0 (Filemaker Inc, Santa Clara, CA). This database will contain all patient information (except names and other identifiers), including the answers to the questionnaire, and the results of the various US imaging modes as well as the pathology results.

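### H2 names no finding-parameter pair, significance level or success rule, its roughly 240–370 imaging-pathology tests have no multiplicity control, and its SHI-versus-HI statement has no test

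*Combined protocol and SAP*

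**What the plan says.** H2 in section 7.2.1 has two parts.

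- The first is existential: "Some findings of SHI (including perfusion estimates and CMI-SHI) or pulse inversion HI correlate with the pathological diagnosis of benign/malignant". It then widens the pathology side with "or with other significant physiological/pathological parameters". The word significant is not defined there.
- The second is comparative: "The fundamental hypothesis is that higher correlation coefficients can be achieved with SHI than with pulse inversion HI". No parameter, margin or test is attached to it.

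Section 7.2.2 sets the scope of testing: "All histopathological variables will be compared to imaging judgments on diagnoses and characteristics of vascularity for the different modalities". Each pair gets a chi-square test, a correlation or a rank test, depending on the types of variable. All analyses are then repeated by racial and ethnic group. Sections 7.2.1 to 7.2.4 describe no multiplicity adjustment.

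Section 7.2.4 gives a two-sided 0.05 level and a power statement for the ROC comparison, H3 and H4. It gives neither for H2.

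**The concern.** The first part of H2 asks only that something on the imaging side be related to something on the pathology side. Both sides are long lists, every pair is to be tested, and nothing limits the error across them. Chance alone will then very probably supply significant pairs, and the plan does not say how many, which ones or how strong they must be. Whoever writes the report can choose the supporting pairs after seeing the results.

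The second part is called the fundamental hypothesis and is the more informative claim. The plan does not say which coefficients are compared or how the difference is tested. Adding CMI-SHI and perfusion on the SHI side gives SHI more chances to produce the largest coefficient.

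At stake are the reported pathological correlates of SHI and the statement that SHI outperforms HI on correlation. The ROC comparison under H1 does not depend on this.

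**Working it through.** **The plan's own figures.** There is none for H2. As a check on method, the nearest correlation calculations in section 7.2.4 do reproduce, using Fisher z for two independent correlations: power = Φ(|z1 − z2| / √(2/(n−3)) − 1.96).

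- H3: 0.57 versus 0.75, n = 152: 80.2%.
- H4: 0.40 versus 0.70, n = 84: 80.6%.

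Both match the stated power of more than 80%.

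**Counting the tests (my count from the text).**

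- Pathology variables, section 6.7: 17. These are diagnosis, ER, PR, HER2, hemorrhagic, necrotic and other component, margins, size, TNM stage, lesion type, vascular invasion, histological grade, cytological grade, metastases, nodes, and percentage invasive or in situ.
- Imaging findings per mode, sections 6.6 and 7.2.3, restricted to diagnosis and vascularity as in section 7.2.2: 7. These are diagnosis, color distribution, color content, vessel irregularity, anastomoses, enhancement pattern and degree of neovascularity.
- Modes relevant to H2: HI and SHI, with CMI-SHI as a possible third. SHI perfusion is one further measure.

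HI and SHI: 7 × 17 × 2 = 238. With perfusion: 238 + 17 = 255. With CMI-SHI as well: (7 × 3 + 1) × 17 = 374. Multiple readers and the race/ethnicity repeats are not counted.

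**Expected false positives at an assumed 0.05 per test, nothing related.** 238 × 0.05 = 11.9; 255 × 0.05 = 12.75; 374 × 0.05 = 18.7.

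**Chance of at least one.** Under independence, 1 − 0.95^238 = 0.999995, and it is higher for 255 and 374. The variables are not independent, so I simulated a global null with correlated normal variables, 2,000 replicates per setting. I used n = 450 and n = 90; the latter is 20% of 450, roughly the number of cancers. Ranges cover both sample sizes.

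| Correlation: between findings / same finding across modes / between pathology variables | 255 tests | 374 tests |
|---|---|---|
| 0.3 / 0.8 / 0.3 | 0.999–1.000 | 1.000 |
| 0.5 / 0.8 / 0.3 | 0.996–0.997 | 1.000 |
| 0.5 / 0.8 / 0.5 | 0.988–0.990 | 0.994–0.997 |
| 0.7 / 0.9 / 0.5 (strong) | 0.948–0.954 | 0.972–0.974 |
| 0.7 / 0.9 / 0.7 (very strong) | 0.860–0.864 | 0.903–0.910 |

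A separate run with correlation 0.9 among all variables gave about 35–41% (for example 0.363 for 320 tests and 0.407 for 480, n = 90).

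**How small a correlation would count.** The smallest nominally significant |r| is t/√(n − 2 + t²), with t the 97.5% point on n − 2 degrees of freedom. This gives 0.207 at n = 90 and 0.092 at n = 450.

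**The SHI-over-HI statement.** In the same null simulations, the largest absolute SHI coefficient exceeded the largest HI coefficient in:

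- 0.480–0.494 of replicates with equal families (238 tests);
- 0.516–0.580 with perfusion on the SHI side (255 tests);
- 0.668–0.712 with CMI-SHI added (374 tests).

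**The case against.** A reader might infer that H2 cannot fail and is almost certain to be declared true. The documents do not support that. They never say when H2 counts as confirmed, and the second statement can fail: judged on the largest coefficients it would fail by chance in roughly 29–52% of null trials. The 0.05 level is my assumption for H2. Under extreme correlation the chance of at least one false positive falls well below certainty.

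A reader might also conclude that support for H2 would carry no evidence. That goes too far. The calculation assumes that no pair is related, yet the family includes the reader's diagnosis against pathological diagnosis. Section 1.1 reports pilot ROC areas of 0.78 for SHI and 0.90 for CMI-SHI, so some associations are probably real, and an individual result could be strong. Lack of error control weakens a claim; it does not empty every result.

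A larger count is tempting as well. Ten features per mode would give 17 × 10 × 2 = 340 tests and 17 expected false positives. That requires features such as size, shape or echogenicity ("Diagnosis; size, shape, and orientation of the lesion; echogenicity compared to surrounding tissue"), while section 7.2.2 confines these comparisons to diagnoses and vascularity. The smaller count is the defensible one, and it still runs to hundreds.

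What stands after all this: no pair, level, success rule or error control for the first statement, and no test for the second.

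**Conclusion.** The concern holds in this limited form. With roughly 240–370 unadjusted tests, about 12–19 nominally significant pairs would be expected if nothing were related. At least one would appear with probability of about 95–100% under moderate to strong correlation, 86–91% under very strong correlation and 35–41% in the extreme case. A single significant pair is therefore weak support for H2's first statement. The second would appear true by chance about 48–71% of the time if judged on the largest coefficients.

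These figures rest on my variable count, on 0.05 per test, on a global null, and on correlated normal data standing in for the mix of chi-square, rank and correlation tests. The correlation levels are assumed, since the documents give none. This is a cheap improvement; it does not threaten the primary comparison.

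**What to change.** Change sections 7.2.1 and 7.2.2 in two places.

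1. Declare the imaging-pathology comparisons one exploratory family. Report each with its estimate, confidence interval and Benjamini-Hochberg adjusted p-value, and claim H2's first statement only for pairs that survive adjustment. Bonferroni is a stricter alternative: 0.05/255 = 0.000196 or 0.05/374 = 0.000134 per test, with a simulated familywise error of 0.017–0.056 across the settings run.
2. Test the SHI-versus-HI statement on one finding-parameter pair measured in both modes and named before readings are linked to pathology. One example is the primary reader's 0–100 rating (sections 6.6 and 7.2.2) against benign/malignant pathology. Use a paired test for dependent correlations, or a paired bootstrap, at two-sided 0.05, because the same patients supply both coefficients. A single named test carries a 5% false-positive risk. The example lies close to the ROC comparison of the same ratings, so the team may prefer a vascularity measure; what matters is naming it in advance.

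I would not reduce H2 to whole-lesion SHI perfusion alone. Section 1.1 reports that "SHI perfusion estimates within the entire lesion were significantly different for malignant and benign tumors" (p = 0.04), but this was one of three regions, the other two having p > 0.32, in a pilot of 16 lesions with 4 cancers. A simple correction gives 3 × 0.04 = 0.12. That choice would also leave HI, and so the SHI-versus-HI statement, untested.

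The cost is wording and a routine adjustment of p-values, with no extra patients, imaging or procedures. The downside is that fewer secondary associations will be called significant.
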